4.3.6 Method of Assigning Subjects to Treatment Groups

Subjects will be assigned according to section 4.1. The first eligible 50 subjects will be assigned by the investigator to Exufiber Ag+, Subjects 51 to 65 will be assigned to Exufiber, Subjects 66 to 85 will be assigned to Aquacel Ag Extra and recorded in the eCRF. Subjects 86 to 105 will be assigned to Exufiber Ag+ on eligible pressure ulcer subjects. Mölnlycke or delegate will notify the study investigator when each treatment group has been fully enrolled. Each treatment group may be adjusted due to enrolment by approximately 20%.

The secondary dressing will be chosen according to local routine.

If a subject discontinues from the investigation, the Subject ID will not be reused and the subject will not be allowed to re-enter the investigation.

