4.7 Statistical Methods and Determination of Sample Size

4.7.1 Statistical Evaluation

General Methodology

The main focus and analysis will be the analysis of the subjects treated with Exufiber Ag+.

The main analyses will be change in primary and secondary efficacy endpoints from baseline to 4 weeks on the ITT population in this group treated with Exufiber Ag+. If missing values at 4 weeks

Title: CIP with integrated central Amendments 1 and 2 ExufiberAg+01

Page 41(50)

Investigation Code	ExufiberAg+01Final Version	Approval date	2017-05-10
		Amendment 1 Approval date	2017-05-26
		Amendment 2 Approval date	2018-08-07
		Amendment 3 Approval date	2018-08-21
		Amendment 4 Approval date	2019-02-19

last observation carry forward (LOCF) will be applied from 1 week.

A sensitivity analysis will be performed for primary analysis with complete cases.

Complementary analyses will be performed on the PP population and for change from baseline to 3 days, 1 week, 2 weeks and 3 weeks.

Since primary efficacy variable and most of the secondary efficacy variables are ordered categorical or dichotomous variables the Sign test will be used for analysis of change within groups for these types of variables and described with number and percentages of improved, not changed and worsened. For primary efficacy variable and important secondary efficacy variables a complete cross tabulation baseline and 4 weeks will be given.

All significance test will be two-sided and conducted at the 5 % significance level.

Continuous variables will be described with mean, SD, median, minimum and maximum and categorical variables will be given with number and percentages. All measured variables will be described by visit.

The statistical analysis of the groups treated with Exufiber or Aquacel Ag Extra will be analysed separately with the same statistical methods as specified above. The database for Exufiber Ag+ will be declared clean and will be analysed before the other two treatment groups are finalised.

Patient Disposition and Data Sets Analysed

The number of subjects included in each of the ITT, PP and safety populations will be summarized. The number and percentage of subjects enrolled and treated will be presented.

Subjects who completed the study and subjects who withdrew from study prematurely will also be presented with a breakdown of the reasons for withdrawal for the ITT, PP and safety populations.

Protocol Violations/Deviations

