4.7.2 Performance Analysis

Primary Performance Analyses

The primary performance analysis will be the analysis of change in Exudate level from baseline to 4 weeks in the Exufiber Ag+ treatment group with the two-sided Sign test on the Intent To Treat (ITT)-population at significance level 0.05. If the 4 weeks value is missing last observation carry forward (LOCF) will be allied from 1 week.

A complementary sensitive analysis will be performed with the same analysis on complete cases. (No imputation)

Secondary Efficacy Analyses

All secondary efficacy variables will be analysed within the treatment groups for the ITT- and Per Protocol (PP) population using the statistical methods given in section general methodology. Primary efficacy variable will also be analysed on the PP-population

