4.7.3 Determination of Sample Size

In the study PUMA 416, with 100 subjects treated with Mepilex without Ag, the result regarding change in Exudate level from baseline to 4 weeks was 56.5 % improved, 32.9 % unchanged and 10.6 % worsened. Assuming the same proportions in this study 38 subjects are needed to find a significant improvement with the Sign test with 95% power and significance level 0.05. If we expect a dropout rate of around 20% we will include 50 subjects in the Exufiber Ag+ treatment group.

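### Do the Sign tests in the small Exufiber and Aquacel Ag Extra groups need to be replaced because those groups were never sized?

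*Combined protocol and SAP*

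**What the plan says.** Section 4.7.1 makes Exufiber Ag+ the main focus. It specifies the Sign test for within-group change in ordered and dichotomous variables, with results "described with number and percentages of improved, not changed and worsened". It also sets the level: "All significance test will be two-sided and conducted at the 5 % significance level". For the other two dressings it says: "The statistical analysis of the groups treated with Exufiber or Aquacel Ag Extra will be analysed separately with the same statistical methods". Section 4.7.2 confines the primary analysis to Exufiber Ag+ and adds: "All secondary efficacy variables will be analysed within the treatment groups".

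Group sizes are in section 4.3.6. The first 50 subjects receive Exufiber Ag+. Then "Subjects 51 to 65 will be assigned to Exufiber, Subjects 66 to 85 will be assigned to Aquacel Ag Extra", which gives 15 and 20. Finally, "Subjects 86 to 105 will be assigned to Exufiber Ag+ on eligible pressure ulcer subjects", which adds 20 and would bring Exufiber Ag+ to 70 if they are pooled with the first 50. The sizes are flexible: "Each treatment group may be adjusted due to enrolment by approximately 20" per cent.

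Section 4.7.3 has one calculation, for one group, ending with: "we will include 50 subjects in the Exufiber Ag+ treatment group". The plan gives no sizing for the other two groups and claims no power for them. Sections 4.7.1 and 4.7.2 mention no confidence intervals and do not say how three separate p-values should be read together.

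**The concern.** The same test at the same level in groups of 50, 15 and 20 makes the chance of significance depend strongly on group size. A reader who sees a significant change with Exufiber Ag+ and none with a comparator could take that as a difference between dressings, when it may reflect only the number of subjects.

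The setting adds some weight. The Introduction describes Exufiber Ag+ favourably against both other dressings, so the three results are likely to be seen side by side. The Exufiber Ag+ database is also to be analysed before the other groups are finalised. At stake would be an unsupported claim about relative performance, although the Exufiber Ag+ test itself is sound.

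**Working it through.** **Inputs.** From section 4.7.3: 56.5% improved, 32.9% unchanged, 10.6% worsened. From section 4.7.1: two-sided Sign test at 0.05. From section 4.3.6: n = 50 (or 70), 15 and 20. Assumptions: the same rates hold in every group, every enrolled subject is analysed, and the groups are independent.

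**Method.** The Sign test drops unchanged subjects. The probability of a change is 0.565 + 0.106 = 0.671, and the probability of improvement given a change is 0.565 / 0.671 = 0.842. The number changed is M ~ Binomial(n, 0.671), and the number improved given M is Binomial(M, 0.842). The test rejects when twice the binomial tail at 0.5 is at most 0.05. Power is averaged over M.

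**The plan's own figure.** At n = 38 this gives 94.6% (39 gives 95.2%), against the stated 95%. Allowing for 20% dropout, 38 / 0.8 = 47.5, so 48, which the plan rounds up to 50. The plan's calculation reproduces.

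**Power by group.**

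| Group | n | Exact power |
|---|---|---|
| Exufiber | 15 | 50.5% |
| Aquacel Ag Extra | 20 | 67.1% |
| Exufiber Ag+ | 50 | 98.7% |
| Exufiber Ag+ with subjects 86 to 105 | 70 | 99.9% |

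With comparators 20% larger (18 and 24), power is 60.9% and 78.3%. With comparators 20% smaller (12 and 16), it is 37.5% and 54.2%. A Sign test by normal approximation without continuity correction gives about 61% at 15 and 76% at 20.

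**Chance of the misleading pattern when all dressings are equal.**

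- Exufiber Ag+ significant, Exufiber not: 0.987 × (1 − 0.505) = 0.49.
- Exufiber Ag+ significant, Aquacel Ag Extra not: 0.987 × (1 − 0.671) = 0.32.
- Exufiber Ag+ significant, at least one comparator not: 0.987 × (1 − 0.505 × 0.671) = 0.65. This is 0.52 with comparators of 18 and 24, and 0.79 with 12 and 16.

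Over common rates of 45–70% improved and 8–15% worsened, the last figure runs from 0.27 (70/8) to 0.78 (45/10). At 70/5, outside that range, comparator power is 88% and 97%, and the pattern occurs about 15% of the time: with Exufiber Ag+ power near 1, 1 − 0.884 × 0.967 = 0.145.

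**Are the small-group tests valid?** Yes. With 10 subjects changed, close to the 15 × 0.671 = 10.1 expected for Exufiber, the exact test rejects at 9 or more changes in one direction. Its error rate is 2 × (10 + 1) / 1024 = 2.1%, below 5%.

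**Would the planned output mislead?** Take near-equal results:

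| Group | Improved | Worsened | Sign test | p |
|---|---|---|---|---|
| Exufiber Ag+ | 28/50 = 56% | 5 | 28 of 33 | 0.00007 |
| Aquacel Ag Extra | 11/20 = 55% | 2 | 11 of 13 | 0.022 |
| Exufiber | 8/15 = 53% | 2 | 8 of 10 | 0.11 |

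The p-values differ widely. The percentages that the plan already requires are 56, 55 and 53, so the similarity is visible. Section 4.7.1 also asks for a full baseline-by-4-week cross-tabulation of the primary variable, and an interval can be computed directly from those counts.

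**The case for a change.** The strongest case for a change is that groups meant to be descriptive are better served by estimates with intervals than by 5% tests with power near 50% and 67%. Percentages alone do not show how little 15 or 20 subjects can establish. Exact intervals and one sentence of interpretation cost almost nothing, and fixing the reading rule before the Exufiber Ag+ result is known has some value. The issue also extends to the secondary variables, which are tested within each group.

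The arithmetic behind this stands, and so does the caution that a non-significant result in a small group says little. The need to amend does not follow. Removing the comparator tests would discard valid, if insensitive, results. Exact intervals for the percentage improved (41–70%, 32–77% and 27–79% in the example) do not match the Sign test: they ignore worsening and have no null value to read against. A matching interval would be for the share improved among those who changed, or for improved minus worsened. Adding a between-dressing difference would introduce the comparison that the concern warns against, in groups filled one after another without randomisation. What remains is a useful reporting courtesy that alters no planned result.

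**Conclusion.** No change to the plan is needed. Supporting groups in a non-randomised investigation need no power calculation, and the plan claims no power for them. Followed exactly, it gives valid within-group results. The primary Exufiber Ag+ test is untouched, and no stated objective depends on comparing dressings.

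The 65% figure is the chance of a pattern of p-values, not of a wrong conclusion. Harm needs the further step of comparing significance across groups, which the documents never propose and which the separate analyses and the non-randomised label discourage. The figure also rests on rates from a different dressing assumed equal in all three groups, on the exact form of the test, and on every enrolled subject being analysed.

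An analyst writing the report can add a suitable interval from the planned counts and note that differing within-group significance is not evidence of a difference between dressings. Neither step requires an amendment.

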4.7.2 Performance Analysis

Primary Performance Analyses

The primary performance analysis will be the analysis of change in Exudate level from baseline to 4 weeks in the Exufiber Ag+ treatment group with the two-sided Sign test on the Intent To Treat (ITT)-population at significance level 0.05. If the 4 weeks value is missing last observation carry forward (LOCF) will be allied from 1 week.

A complementary sensitive analysis will be performed with the same analysis on complete cases. (No imputation)

Secondary Efficacy Analyses

All secondary efficacy variables will be analysed within the treatment groups for the ITT- and Per Protocol (PP) population using the statistical methods given in section general methodology. Primary efficacy variable will also be analysed on the PP-population

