4.2.4 Withdrawal of Subjects from Treatment or Assessment

Subjects are free to discontinue participation in the investigation at any time, and without prejudice to further treatment. Subjects who discontinue the investigation should always be asked about the reason(s) for their discontinuation and about the presence of any Adverse Event/Adverse Device Effect or Device Deficiency and, if possible, be assessed by an investigator. Adverse Event/Adverse Device Effect should be followed up.

Subjects may be withdrawn from investigation treatment and assessments at any time, at the discretion of the investigator.

Incorrectly enrolled subjects will be withdrawn from further investigation treatment and assessments. A subject may, however, continue the investigation under special circumstances (i.e. if continuation of investigation treatment or follow-up actions are necessary for the subject's safety and well-being, or if only a follow-up period remains, and the continuation of the investigation is not expected to be associated with any risk or discomfort for the subject).

Clinical Investigation Plan

Document ID: PD-523857 Rev: 01

Title: CIP with integrated central Amendments 1 and 2 ExufiberAg+01

Page 25(50)

Investigation Code	ExufiberAg+01Final Version	Approval date	2017-05-10
		Amendment 1 Approval date	2017-05-26
		Amendment 2 Approval date	2018-08-07
		Amendment 3 Approval date	2018-08-21
		Amendment 4 Approval date	2019-02-19

Title: CIP with integrated central Amendments 1 and 2 ExufiberAg+01

Page 26(50)

Investigation Code	ExufiberAg+01Final Version	Approval date	2017-05-10
		Amendment 1 Approval date	2017-05-26
		Amendment 2 Approval date	2018-08-07
		Amendment 3 Approval date	2018-08-21
		Amendment 4 Approval date	2019-02-19

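### LOCF and the complete-case sensitivity analysis can both miss subjects withdrawn for wound deterioration, so agreement between them gives no reassurance about the primary result

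*Combined protocol and SAP*

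**What the plan says.** Section 4.7.2 tests change in exudate level from baseline to 4 weeks in the Exufiber Ag+ group "with the two-sided Sign test on the Intent To Treat (ITT)-population at significance level 0.05". On missing data it says: "If the 4 weeks value is missing last observation carry forward (LOCF) will be allied from 1 week". On robustness it says: "A complementary sensitive analysis will be performed with the same analysis on complete cases", without imputation.

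Other provisions that bear on the point:

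- Section 4.2.4: "Subjects may be withdrawn from investigation treatment and assessments at any time, at the discretion of the investigator". Subjects who discontinue are to be asked why and, where possible, assessed by an investigator.
- Section 4.7.1 reports premature withdrawals "with a breakdown of the reasons for withdrawal", by analysis population. The reasons do not enter any analysis of the endpoint.
- Section 4.5.2 treats dry and healed wounds as successes. There is no matching rule for failures.
- Sections 2 and 4.1 let follow-up end before Visit 5 when the wound is dry or healed.
- Sections 4.7.1 and 4.7.2 add a per-protocol analysis and analyses at earlier time points. Neither scores a withdrawal as a failure.

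**The concern.** The Sign test uses only the numbers improved and worsened; unchanged subjects drop out. Take a subject whose exudate grade at the carried visit equals baseline and who is later withdrawn because the wound deteriorates. LOCF makes that subject a tie, which the test ignores, and the complete-case analysis omits the subject. The two analyses then use identical counts. If the carried grade was better than baseline, LOCF counts the subject as improved. In neither case does the failure reach the worsened column.

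The sensitivity analysis therefore cannot reveal this particular weakness of the main one. The design offers no other safeguard: the study is non-randomised and each dressing group is analysed separately, so no concurrent comparison would absorb a bias that is common to the arms. At stake is whether a significant within-group improvement can be taken at face value if many dropouts are failures.

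**Working it through.** **Inputs from the plan (4.7.1, 4.7.3).** "All significance test will be two-sided and conducted at the 5 % significance level". Assumed outcome: "56.5 % improved, 32.9 % unchanged and 10.6 % worsened". Sample size: "38 subjects are needed to find a significant improvement with the Sign test with 95% power and significance level 0.05", raised to 50 for about 20% dropout.

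**Assumption not in the documents.** The true status of dropouts. It is varied below from none to all failed.

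**1. Reproducing the plan's figure.** Exact power with the number of non-tied subjects m ~ Bin(N, 0.565 + 0.106 = 0.671), the number improved given m ~ Bin(m, 0.565/0.671 = 0.842), and rejection when the exact two-sided binomial p ≤ 0.05. N=38 gives power 0.946; N=39 gives 0.952. The stated 38 is reproduced to within one subject. Dropout: 38/0.8 = 47.5, so 48, consistent with 50.

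**2. Expected counts at N=50, 20% dropout.** 40 completers: improved 40 × 0.565 = 22.6 ≈ 23; worsened 40 × 0.106 = 4.2 ≈ 4; unchanged 13. Ten subjects lack a 4-week value.

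**3. Sign test under different scorings.** p = 2 × P(X ≤ smaller count), with X ~ Bin(improved + worsened, 0.5). In the failure-scored rows, dropouts not scored as worsened are treated as ties.

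| Scoring of the 10 dropouts | Improved v worsened | p |
|---|---|---|
| Complete cases | 23 v 4 | 0.0003 |
| LOCF, all carried as unchanged | 23 v 4 | 0.0003 |
| LOCF, same proportions as completers | 29 v 5 | 0.00004 |
| 6 worsened | 23 v 10 | 0.035 |
| 7 worsened | 23 v 11 | 0.058 |
| All 10 worsened | 23 v 14 | 0.19 |

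The first two rows are identical, which is the core of the point. The tipping point is 7 of 10.

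**4. Other dropout rates and sizes.**

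- N=50, 10% dropout (45 completers: 25 improved, 5 worsened), all 5 dropouts worsened: 25 v 10, p=0.017, still significant.
- N=50, 30% dropout (35 completers: 20 improved, 4 worsened), all 15 worsened: 20 v 19, p=1.0.
- Section 4.3.6 assigns subjects 86 to 105 to Exufiber Ag+ as well. If these 20 are pooled, N=70. At 20% dropout, 56 completers give 32 v 6. With 11 of 14 dropouts worsened, 32 v 17, p=0.044; with 12, 32 v 18, p=0.065; with all 14, 32 v 20, p=0.13. The tipping point is 12 of 14.

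**5. Power if failures are scored as worsened (20% dropout, half of dropouts failing).** If the other dropouts are unchanged, P(improved) = 0.8 × 0.565 = 0.452 and P(worsened) = 0.8 × 0.106 + 0.1 = 0.185. Power at N=50 is 0.60. If the other dropouts behave like completers, the probabilities are 0.452 + 0.1 × 0.565 = 0.509 and 0.185 + 0.1 × 0.106 = 0.195, and power is 0.72. At N=70 the range is 0.78 to 0.87.

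**6. Chance of a false claim in an adverse scenario.** Assume no true effect, with improved = worsened = (1 − 0.329)/2 = 0.3355, N=50, and every dropout truly worsened. Counting every outcome, the chance of significant improvement is 1.6%. Under complete cases, or LOCF with dropouts carried as unchanged, it is 10.8% at 10% dropout and 46.6% at 20%. If all dropouts were already worse at the carried visit, LOCF stays at 1.6%.

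**The case against.** A reader might infer that LOCF removes treatment failures as such. It does not: a subject already worse than baseline at the carried visit is counted as worsened. Section 4.2.4 also asks for an assessment at discontinuation where possible, although it does not name the exudate grade or say that it would be used. Failures are lost only when the carried grade is equal or better, or when no usable grade exists.

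A reader might also infer that both analyses lean in favour of the dressing. The documents do not support that. Wounds that become dry or heal end follow-up early, and no rule says how they enter the 4-week analysis. Complete cases could drop these successes, which would count against the dressing.

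The mechanism is possible rather than documented. Withdrawal is at the investigator's discretion, and no section requires it for worsening or infection, so deteriorating wounds may stay in the study and be graded at 4 weeks. The tipping points are high, and the reported withdrawal reasons, the analyses at earlier visits and the baseline-by-4-weeks cross-tabulation would disclose part of the problem.

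All of this stands and limits the claim. It does not close the gap, because disclosure is not a test and no planned analysis scores a withdrawal for deterioration as a failure.

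**Conclusion.** The point holds in a limited form: LOCF and complete cases can both miss failures, so their agreement is not evidence of robustness. At the plan's own 20% dropout and outcome proportions, p can move from 0.0003 to 0.19, but significance is lost only when at least 7 of 10 dropouts are failures, or 12 of 14 if the added subjects are pooled. At 10% dropout the primary result survives the worst case.

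It would go too far to conclude that the primary result is likely to be falsely positive. The lower power figures describe a stricter scoring under a real effect; they are not a false-positive rate. The 46.6% figure needs a true null and every dropout worsened. The net direction of bias is unknown.

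The conclusion rests on an assumed share of failures among dropouts, for which the documents give no figure. A prespecified tipping-point analysis is useful for that reason. The change is worth making, but it does not invalidate the primary analysis.

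**What to change.** In section 4.7.2, add a prespecified sensitivity analysis on the ITT population using the same two-sided Sign test:

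- Subjects withdrawn for wound-related reasons (target-wound infection or deterioration, device-related adverse event, lack of effect) count as worsened. They take a negative sign even if the baseline grade was Leaking, since the scale leaves no room to worsen from there.
- Adverse events unrelated to the device or the target wound are not scored as worsened. The definition in section 9 covers any untoward occurrence, so using all adverse events would turn unrelated illness into exudate failure.
- Subjects whose follow-up ended early because the wound was dry or healed count as improved, in line with section 4.5.2.
- Report the tipping point: the number of dropouts that must be failures before p exceeds 0.05.

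The same edit should state whether LOCF uses the 1-week value only or the last value from 1 week onward, and what happens when no such value exists. It should be fixed before the Exufiber Ag+ database is declared clean, which section 4.7.1 places ahead of the other groups.

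The cost is one extra table from data already collected (withdrawal reasons, device causality of adverse events, infection signs), and a supporting result that may be less favourable.
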